### 9. RESEARCH METHODS

#### 9.1. Study Design

This structured secondary data collection study will be a retrospective cohort study using Centers for Medicare and Medicaid Services (CMS) Medicare data to examine the effect of PCV13 receipt on the risk of MACE among adults aged  $\geq 65$  years in the United States. Individuals will be identified using Medicare Fee-for-Service (FFS) Parts A and B enrollment and claims data.

The analysis will be conducted at the time-segment level using a target trial emulation approach. In this time-segment design, individuals who receive a PCV13 vaccine during the study period can contribute up to two time segments during the follow-up period: a PCV13 unvaccinated time segment and a PCV13 vaccinated time segment. Each segment will be attributed to the appropriate vaccination exposure status cohort, resulting in the individual having two separate index dates included in the analysis. Inclusion/exclusion criteria and baseline characteristics will be assessed separately for these two index dates. For PCV13 unvaccinated patients, multiple eligible times may be identified within the study period, but only the first eligible time will be selected due to the large sample size of the unvaccinated cohort. Individuals who remain unvaccinated throughout the entire follow-up period can contribute a maximum of 1 time segment, which will be attributed to the unvaccinated cohort. All analyses will be conducted based on time-segment level data, which allows the exposure variable – PCV13 vaccination – to be treated as time-invariant within each segment.

The index date for the vaccinated cohort is defined as the date of first PCV13 vaccination. For the unvaccinated cohort, the index date is defined as the date of the first available healthcare claim that occurs after the eligibility date (September 14, 2014) and ensures a six-month period of continuous enrollment prior to the index date. Eligible vaccinated and unvaccinated index dates are 1) between September 14, 2014 and November 30, 2019 and 2) after the individual has at least 6 months of continuous enrollment in Medicare FFS Parts A and B. The 6 months of continuous enrollment prior to the index date for each time segment will be used as the baseline period. Baseline covariates, including demographics, preventative care behaviors, and comorbidities will be assessed during this period.

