# 9.2. Setting

The study period is September 14, 2014 through December 31, 2019. However, Medicare data will be used going back to 1) September 14, 2013 to assess baseline characteristics and 2) January 1, 2010 to ascertain whether the individual received a PCV13 or PPSV23 vaccine prior to the study period.

The study population includes individuals aged  $\geq 65$  years and enrolled in Medicare Fee-for-Service (FFS) Parts A and B as of September 14, 2014. Individuals are required to have at least 6 months of prior continuous enrollment in Medicare FFS Parts A and B as of the index date to be included in the study. Individuals with evidence of PCV13 receipt prior to the index date, evidence of PPSV23 receipt in the 365 days prior to the index date, enrollment in Medicare Part C between September 14, 2014 and the index date, a high-risk condition for CAP in the 365 days prior to index, iatrogenic immunosuppression in the 6 months prior to index, a pneumonia diagnosis code in the hospital setting in the 365 days prior to index, a MACE event in the hospital, skilled nursing facility (SNF), or long-term care facility (LTCF) setting in the 365 days prior to index will be excluded. PCV13 vaccinated individuals with a pneumonia diagnosis code in the hospital setting or a MACE diagnosis code in the hospital, SNF, or LTCF setting in the 13 days following first PCV13 vaccination will also be excluded.

For PCV13 vaccinated individuals contributing unvaccinated and vaccinated time segments, inclusion and exclusion criteria will be assessed separately for each index date.

Inclusion criteria rationale:

- Individuals were required to be enrolled in Medicare FFS Parts A and B because that is the database being used for the study. Individuals were required to be enrolled as of September 14, 2014 so that the analysis would not misclassify an individual as unvaccinated if the individual received their PCV13 vaccine after the ACIP recommendation, but prior to enrolling in Medicare FFS (i.e. vaccination claims will only be included in the database if the vaccine was received while the individual was enrolled in Medicare FFS).
- The study includes adults age ≥65 years as of September 14, 2014 because that is the date that the CDC ACIP gave the age-based PCV13 recommendation for adults age ≥65 years. As such, these adults would have been eligible to receive the PCV13 vaccine (i.e. exposure of interest).

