# 9.2.2. Exclusion Criteria

Patients meeting any of the following criteria as of the index date will not have the respective time segment included in the study:

- 1. Evidence of PCV13 vaccination prior to the index date
- 2. Evidence of PPSV23 vaccination in the 365 days prior to the index datea
- 3.  $\geq 1$  diagnosis code for a high-risk condition in the 365 days prior to the index datea
- 4. Evidence of iatrogenic immunosuppression in the 6 months prior to the index date
- 5. Pneumonia diagnosis code in the hospital setting in the 365 days prior to the index datea
- 6. MACE diagnosis code in the hospital, SNF, or LTCF setting in the 365 days prior to the index datea
- 7. Medicare Part C enrollment between September 14, 2014 and the index date
- 8. PCV13 vaccinated individuals with a pneumonia diagnosis code in the hospital setting or a MACE diagnosis code in the hospital, SNF, or LTCF setting in the 13 days after first PCV13 vaccination

a. For adults with  $\geq 6$  months, but less than 365 days of prior continuous enrollment, the exclusion criteria will be evaluated during the continuous enrollment period that the adult has available.

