Outpatient heart failure	Patient characteristics	Any code for heart failure in the outpatient setting in the 365 days prior to the index date.	Baseline
Coronary artery disease (CAD)	Patient characteristics	Any code (any setting) for coronary artery disease (CAD) in the 365 days prior to the index date.	Baseline
Hypertension	Patient characteristics	Any code (any setting) for hypertension in the 365 days prior to the index date.	Baseline
Valvular heart disease	Patient characteristics	Any code (any setting) for valvular heart disease in the 365 days prior to the index date.	Baseline
Unstable angina	Patient characteristics	Any code (any setting) for unstable angina in the 365 days prior to the index date.	Baseline

CT24-WI-GL02-RF02 6.0 Non-Interventional Study Protocol Template For Secondary Data Collection Study Page 28 of 53

Stable angina	Patient characteristics	Any code (any setting) for stable angina in the 365 days prior to the index date.	Baseline
Aortic aneurysm and dissection	Patient characteristics	Any code (any setting) for aortic aneurysm and dissection in the 365 days prior to the index date.	Baseline
Arrhythmia	Patient characteristics	Any code (any setting) for arrhythmia in the 365 days prior to the index date.	Baseline
Atrial fibrillation	Patient characteristics	Any code (any setting) for atrial fibrillation in the 365 days prior to the index date.	Baseline
Cardiomyopathy	Patient characteristics	Any code (any setting) for cardiomyopathy in the 365 days prior to the index date.	Baseline
Peripheral arterial disease (PAD)	Patient characteristics	Any code (any setting) for peripheral arterial disease (PAD) in the 365 days prior to index	Baseline
Pulmonary hypertension	Patient characteristics	Any code (any setting) for pulmonary hypertension in the 365 days prior to the index date.	Baseline
Rheumatic heart disease	Patient characteristics	Any code (any setting) for rheumatic heart disease in the 365 days prior to the index date.	Baseline
Congenital heart defects	Patient characteristics	Any code (any setting) for congenital heart defects in the 365 days prior to the index date.	Baseline
High cholesterol	Patient characteristics	Any code (any setting) for high cholesterol in the 365 days prior to the index date.	Baseline
High triglycerides	Patient characteristics	Any code (any setting) for high triglycerides in the 365 days prior to the index date.	Baseline

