Physical/wellness visit	Patient characteristics	A CPT or diagnosis code for a wellness visit in the 365 days prior to index.	Baseline
Number of hospitalizations in the prior 180d	Patient characteristics	
 
Count of unique days with an acute hospital admission in the 180 days prior to index
 
Dichotomous, yes/no
 
Continuous statistics including mean, standard deviation (SD), median (Q1 Q3), minimum, and maximum
 
	Baseline
Number of outpatient visits in the prior 180d	Patient characteristics	Count unique days with an outpatient visit in the 180 days prior to index	Baseline
		
 
Dichotomous, yes/no
 
Continuous statistics including mean, standard deviation (SD), median (Q1 Q3), minimum, and maximum
 
	
Nursing home stay	Patient characteristics	Any claim with care location of nursing home in the 365 days prior to index.	Baseline
Skilled nursing facility (SNF) stay	Patient characteristics	Any claim with care location of SNF in the 365 days prior to index.	Baseline
Influenza vaccine	Patient characteristics	Baseline influenza vaccination status: One claim (NDC or CPT) for influenza vaccine of any type in the 365d prior to index.	Baseline and follow-up
		Time-varying influenza vaccination status during follow-up : Patients will be identified and can transition between periods of influenza vaccine exposure and non-exposure throughout the study period. Individuals will be classified as vaccinated starting 15 days after their first claim for an influenza vaccine during each respiratory season and considered vaccinated until the end of that respiratory season.	

CT24-WI-GL02-RF02 6.0 Non-Interventional Study Protocol Template For Secondary Data Collection Study Page 31 of 53

		The 1-year mediation analysis will adjust for baseline influenza vaccination status only.	
Type of index influenza vaccine administered	Patient characteristics	Categories include: Enhanced, standard, and unknown influenza vaccine type	Baseline
PPSV23 receipt	Patient characteristics	One claim (NDC or CPT) for a PPSV23 vaccine between 1 year and 5 years prior to the index date.	Baseline
Respiratory failure	Patient characteristics	Any code (any setting) within the prior 365 days for respiratory failure. Prior respiratory failure will be included as a descriptive variable only.	Baseline
Influenza infection	Patient characteristics	≥1 ICD-9-CM or ICD-10-CM code for influenza in 365 days prior to index	Baseline

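### Section 9.1 sets a 6-month baseline but Table 5 looks back 365 days, and footnote a leaves exclusion look-back unequal, mainly in unvaccinated segments; the net bias is unquantified and probably modest

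*Protocol*

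**What the plan says.** Section 9.1 defines the baseline: "The 6 months of continuous enrollment prior to the index date for each time segment will be used as the baseline period". It adds: "Baseline covariates, including demographics, preventative care behaviors, and comorbidities will be assessed during this period". The inclusion rationale in Section 9.2 gives the 6-month enrollment rule the same purpose.

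Table 5 (Section 9.3.5) labels its rows as baseline but uses a longer window for nearly all comorbidity, care-use and test covariates. Typical rows read "Any code (any setting) for hypertension in the 365 days prior to the index date" and "Any code for heart failure in the outpatient setting in the 365 days prior to the index date". The exceptions are the two visit counts (for example "Count of unique days with an acute hospital admission in the 180 days prior to index") and PPSV23 receipt, taken from 1 to 5 years before index. Section 9.2 opens the data on "September 14, 2013 to assess baseline characteristics", which fits a 365-day window.

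In Section 9.2.2 the PPSV23, high-risk-condition, pneumonia and MACE exclusions also use a year; the last reads "MACE diagnosis code in the hospital, SNF, or LTCF setting in the 365 days prior to the index date". The immunosuppression exclusion uses 6 months. For people with at least 6 months but under 365 days of enrollment, footnote a says "the exclusion criteria will be evaluated during the continuous enrollment period that the adult has available". Table 5 has no matching rule. Section 9.8 treats the absence of a code as absence of the condition.

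**The concern.** Two independent programmers, as Section 9.8 plans, could build different covariates from this text. That needs correcting whatever its numerical effect.

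The second issue is comparability. The exclusion rationale in Section 9.2 says that removing people with recent hospital pneumonia or recent MACE makes that risk the same in the two cohorts. This holds only if the past year is visible for everyone. A person with 6 months of history passes the exclusion if the event was 7 to 12 months earlier. If short histories are more common in one arm, the exclusions work less well there. Under the Table 5 reading the covariates are also less complete there. Standardized mean differences compare recorded values only, so the planned balance check would not show this, and weighting cannot restore a condition that was never recorded.

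**Working it through.** The protocol gives no figure for this point, so there is nothing to reproduce. The check compares the windows, then the dates, then the likely size.

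**1. The two readings**
- *Table 5 governs.* The covariate window is 365 days for people with a year of enrollment and 6 to 12 months for the rest. The missing part is coded as no condition.
- *Section 9.1 governs.* The covariate window is 6 months for everyone: equal, but about half as long.
- *Exclusions.* Under either reading, four of them use 365 days where available and less where not.

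**2. Who has a short look-back**
- From 14 September 2013 to 14 September 2014 is 365 days.
- Section 9.2.1 requires enrollment on 14 September 2014. With continuous enrollment, any index date from 14 September 2015 on has a full year behind it.
- Short histories therefore need both enrollment in the year before 14 September 2014 (or re-enrollment after a gap) and an early index date.
- The unvaccinated index is the earliest healthcare claim once 6 months are reached, and only the first eligible time is used, so it falls early by rule. The vaccinated index is the dose date, anywhere in the 1,903 days to 30 November 2019.

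**3. Simulated look-back**

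I applied these index rules to 1,000,000 simulated people per scenario. The following are assumptions, except where a source is named:
- 3%, 5% or 8% enrolled uniformly over the year before 14 September 2014; the rest long before.
- The mean wait to the next claim is 15, 45 or 120 days.
- 39.6% of people are vaccinated (the proportion in Section 9.5), with two further runs at 66% (0.396/0.604, treating 39.6% as a share of segments).
- Dose dates are uniform over the index period or front-loaded (exponential, mean 500 days).

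Ranges over all scenarios:
- Recent enrollees with under 365 days of look-back: 64-96% of their unvaccinated segments and 7-23% of their vaccinated segments.
- Of all short-look-back segments, 85-97% were unvaccinated.
- Share of the whole cohort affected: 1.9-7.6% of unvaccinated and 0.2-1.7% of vaccinated segments.
- Median look-back in recent enrollees' unvaccinated segments: 216-322 days.

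Hand check of the first range: 0.03 × 0.64 = 1.9%, and 0.08 × 0.96 = 7.7%, close to the simulated 7.6%.

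**4. What a short look-back misses**

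With uniform event timing, a look-back of L days misses (365 − L)/365 of prior-year events:
- L = 183 (worst case): 182/365 = 50%
- L = 216: 149/365 = 41%
- L = 322: 43/365 = 12%

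For a condition coded at a constant rate, with probability p of appearing in 365 days, the probability in 183 days is 1 − (1 − p)^(183/365):
- p = 0.3 gives 0.164
- p = 0.5 gives 0.294
- p = 0.7 gives 0.453
- p = 0.9 gives 0.685

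This is the loss for people at the 6-month minimum if Table 5 governs, and for everyone if Section 9.1 governs.

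**5. Rough size for the MACE exclusion alone**

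Take the control hazard of 0.0507 per year (Section 9.5) as the prior-year MACE rate. This is an assumption; an unselected rate may be higher.
- High end: 0.0507 × 0.5 × 0.076 = 0.19% of unvaccinated segments carry an unseen event.
- Low end: 0.0507 × 0.12 × 0.019 = 0.01%.
- If such people had five times the hazard (assumption), the unvaccinated hazard rises by 4 × 0.19% = 0.8% at most and by about 0.05% at least. The plan's assumed hazard ratio is 0.85.

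The effect of under-recorded covariates is not covered by this figure.

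**The case against.** The strongest reply has four parts.

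- *The operative reading is recoverable.* Table 5 holds the variable-level definitions, and the data start date in Section 9.2 fits 365 days. This makes Table 5 the likelier intention, but Section 9.1 still says otherwise, and Table 5 has no rule for people with less than a year.
- *Footnote a is a declared rule, not an oversight.* That is true, and a common shorter look-back or a sensitivity analysis requiring 365 days would be alternatives. Declaring the rule does not make ascertainment equal, and it works against the stated reason for the exclusions.
- *The contradiction does not itself cause unequal covariates.* This stands. A reader might infer that the mismatch under-records comorbidity in the unvaccinated arm. That follows only if Table 5 governs. Only the exclusion look-back is unequal under both readings.
- *The direction is not settled.* A reader might also infer that the bias favours PCV13. Hidden comorbidity and missed prior MACE would tend that way. But the 365-day covariates also include influenza vaccination, wellness visits and laboratory tests, and under-recording those hides healthy behaviour in the unvaccinated arm. A missed PPSV23 dose 7 to 12 months earlier may leave protected people there. Both may act against PCV13, and the documents do not allow a net sign.

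**Conclusion.** The conflict between Section 9.1 and Table 5 is real and must be resolved. The unequal exclusion look-back follows from the 6-month enrollment rule and footnote a under either reading. Its concentration in unvaccinated segments is not stated in the protocol, but it follows from the index rules and held in every scenario tried.

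The size is limited. The documents give no count of recent enrollees, so the 2-8% of unvaccinated segments rests on the assumed 3-8% of the cohort. Missing half of prior-year events is the extreme at exactly 6 months of history, not the typical case. If Table 5 governs, the shift in the overall hazard ratio is probably modest, and neither its size nor its sign is established. If Section 9.1 governs, the cost is different: weaker confounder measurement in the whole cohort. The point merits a correction but does not show that the primary result would be invalid.

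**What to change.** - Require 365 days of continuous FFS Parts A and B enrollment before every index date. The unvaccinated index becomes the earliest healthcare claim after that point.
- State a 365-day baseline in Section 9.1 and name the exceptions: the two 180-day counts, PPSV23 receipt at 1 to 5 years, and immunosuppression at 6 months. Align the inclusion rationale in Section 9.2.
- Delete footnote a.
- Report the number of segments dropped, by arm.

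The cost is protocol wording and some recent enrollees. The loss is not symmetric: an unvaccinated index can move to a later claim, but someone vaccinated before reaching 365 days of enrollment loses the vaccinated segment. For precision this is negligible against about 25 million eligible and a largest required size of 36,485. The rule does not complete the 1-to-5-year PPSV23 covariate for people enrolled for less than five years; the text should say so.

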#### PFIZER CONFIDENTIAL

CT24-WI-GL02-RF02 6.0 Non-Interventional Study Protocol Template For Secondary Data Collection Study Page 16 of 53 2) disenrollment, 3) death, 4) receipt of a second PCV13 vaccine, 5) receipt of a PPSV23 vaccine, or 6) the end of the study period.

Rationale: A retrospective cohort study design was selected because the PCV13 vaccine was recommended by the Advisory Committee on Immunization Practices (ACIP) for all adults age  $\geq$ 65 years in the United States in 2014. Data on PCV13 eligible individuals with 3 years of follow-up already exists in the Medicare database, which means that the data does not need to be collected prospectively. Additionally, a retrospective cohort was selected instead of a case control design because 1) major cardiovascular events are not considered a rare outcome and 2) a cohort design establishes the temporal relationship between the exposure and outcome. PCV13-vaccinated and PCV13-unvaccinated were selected as the comparison groups because is the comparison that would allow the study to evaluate the impact of PCV13 receipt on risk of MACE.

# 9.2. Setting

The study period is September 14, 2014 through December 31, 2019. However, Medicare data will be used going back to 1) September 14, 2013 to assess baseline characteristics and 2) January 1, 2010 to ascertain whether the individual received a PCV13 or PPSV23 vaccine prior to the study period.

The study population includes individuals aged  $\geq 65$  years and enrolled in Medicare Fee-for-Service (FFS) Parts A and B as of September 14, 2014. Individuals are required to have at least 6 months of prior continuous enrollment in Medicare FFS Parts A and B as of the index date to be included in the study. Individuals with evidence of PCV13 receipt prior to the index date, evidence of PPSV23 receipt in the 365 days prior to the index date, enrollment in Medicare Part C between September 14, 2014 and the index date, a high-risk condition for CAP in the 365 days prior to index, iatrogenic immunosuppression in the 6 months prior to index, a pneumonia diagnosis code in the hospital setting in the 365 days prior to index, a MACE event in the hospital, skilled nursing facility (SNF), or long-term care facility (LTCF) setting in the 365 days prior to index will be excluded. PCV13 vaccinated individuals with a pneumonia diagnosis code in the hospital setting or a MACE diagnosis code in the hospital, SNF, or LTCF setting in the 13 days following first PCV13 vaccination will also be excluded.

For PCV13 vaccinated individuals contributing unvaccinated and vaccinated time segments, inclusion and exclusion criteria will be assessed separately for each index date.

Inclusion criteria rationale:

- Individuals were required to be enrolled in Medicare FFS Parts A and B because that is the database being used for the study. Individuals were required to be enrolled as of September 14, 2014 so that the analysis would not misclassify an individual as unvaccinated if the individual received their PCV13 vaccine after the ACIP recommendation, but prior to enrolling in Medicare FFS (i.e. vaccination claims will only be included in the database if the vaccine was received while the individual was enrolled in Medicare FFS).
- The study includes adults age ≥65 years as of September 14, 2014 because that is the date that the CDC ACIP gave the age-based PCV13 recommendation for adults age ≥65 years. As such, these adults would have been eligible to receive the PCV13 vaccine (i.e. exposure of interest).
- Individuals were required to have at least 6 months of prior continuous enrollment in Medicare FFS prior to the index date to assess baseline characteristics.

